#### 4.2.5.2 Secondary safety variable

The secondary safety endpoint of time to first MACE or other serious CV events of interest will be analyzed using the same method as the primary safety endpoint using a 95% CI and without statistical testing for NI (NI margin will not be used).

Supportive listings will be provided for all adjudicated events with adjudication conclusions.

#### 4.2.5.3 Adverse Events

High-level summaries of AEs and TEAEs will be presented separately. The tables will include the number and percentage of patients for the following categories:

- Any AE/TEAE
- Any AE/TEAE with outcome = death
- Any SAE/TEAE
- Any AE/TEAE leading to discontinuation of IP

Summaries on event counts will also be presented by categories above.

The number and percentage of patients reporting any TEAE will be summarized

- by system organ class (SOC), high level term (HLT), and PT;
- by SOC, HLT, PT, and severity;
- by SOC, HLT, PT, and relationship to the IP

If more than one AE is coded to the same PT for the same patient, the patient will be counted only once for that PT using the most severe and most related occurrence in the summarization by severity and by causal relationship to the IP.

The incidence of common ( $\geq x\%$  of patients in any treatment group, 'x' to be determined prior to the DB lock) TEAEs will be summarized by PT (sorted by decreasing frequency of PT [total]).

All AEs will be provided in a by-patient listing which will include both the term reported on the eCRF (verbatim term) and the PT and SOC to which it is coded. Relative start and stop days will be included along with the actual onset and resolution dates.

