## **3.5.2 Adverse events**

Adverse events will be coded using the MedDRA version 18.0 or newer.

Adverse event data will be categorized according to their onset date, as occurring during washout/run-in, during on treatment, or during off treatment.

An AE will be considered a treatment-emergent adverse event (TEAE) if it started on or after the date of the first dose of double-blind IP or it started before the date of the first dose of double-blind IP and continued during the study with increased severity. An AE that occurs more than 15 days after the date of the last dose of double-blind IP will not be counted as a TEAE.

A TEAE with cause Reasonable Possibility related to the double-blind IP as judged by the investigator is defined as a treatment related AE.

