## **4. ANALYSIS METHODS**

### **4.1 General principles**

Unless otherwise stated, descriptive summaries will be presented by treatment group. The treatment groups will be presented in the order of Acridinium 400 µg and Placebo in tables.

Continuous data will be summarized in terms of the number of nonmissing observations (n), mean, standard deviation (SD), median, minimum, and maximum, unless otherwise stated. Where data are collected over time, both the observed data and change from baseline (refer to Section 3.1.3 for baseline definitions) will be summarized at each time point.

The minimum and maximum will be reported to the same number of decimal places as the raw data recorded in the database, unless a decision has been made to report the summary statistics to a lesser number of decimal places than the original data. Unless otherwise specified in the actual table shells, the mean, SD, standard error of the mean (SEM), median, the upper and the lower limits of confidence interval (CI) will be displayed to the one more decimal place than the raw data in the database. In general, the maximum number of decimal places reported shall be three for any summary statistic.

Categorical data will be summarized in terms of the number of patients providing data at the relevant time point (n), frequency counts and percentages. Any planned collapsing of categories will be detailed in the SAP text and the data displays.

Percentages will be presented to one decimal place. A percentage of 100% will be reported as 100%. Percentages will not be presented for zero counts. Unless otherwise stated, percentages will be calculated using n as the denominator.

Changes from baseline in categorical data will be summarized using shift tables where appropriate.

P-values greater than or equal to 0.001, in general, will be presented to three decimal places. P-values less than 0.001 will be presented as “<0.001”. P-values greater than 0.999 will be presented as “>0.999”.

All report outputs will be produced using SAS® version 9.2 or a later version in a secure and validated environment.

All statistical tests will be two-sided hypothesis tests performed at a 0.05 significance level for main effects. All CIs will be two-sided 95% CIs, unless otherwise stated.

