#### **Deaths, Serious Adverse Events, and Other Significant Adverse Events**

An SAE that occurs on or after the date of the first dose of double-blind IP and within 15 days of the date of the last dose of double-blind IP will be considered an on-treatment SAE/TEAE.

An SAE that occurs after 15 days of the date of the last dose of double-blind IP will be considered an off-treatment SAE.

The following summaries will be produced:

- Number and percentage of patients with any SAEs by SOC, HLT, and PT
- Number and percentage of patients with adverse events with outcome of death by SOC and PT
- Number and percentage of patients with off-treatment SAEs by SOC, HLT, and PT
- Number and percentage of patients with AEs leading to premature discontinuation of the IP by SOC and PT

In addition, separate listings will be provided for the following:

- Deaths
- SAEs
- Permanent discontinuations of study treatment due to AEs

Adjudicated MACEs and other serious CV events of interest will be summarized as follows:

- Number, percentage, and incidence (per 1000 patient-years of exposure to IP) of patients with adjudicated MACE by MACE category, adjudicated subcategory, and PT (on-study analysis and on-treatment analysis).
- Number, percentage, and incidence (per 1000 patient-years of exposure to IP) of patients with adjudicated cardiac disorders (i.e. cardiac arrhythmias SMQ and cardiac failure SMQ) and cerebrovascular disorders by specific SMQ category and PT (on-study analysis and on-treatment analysis).
- Number, percentage, and incidence (per 1000 patient-years of exposure to IP) of patients with adjudicated non-fatal other CV events by PT (on-study analysis).

Supportive listings to summaries described above will be provided.

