#### **Adverse events of special interest (AESI)**

The summaries on the following AESI will be produced by SOC and PT.

Events of interest	Standard MedDRA Query Category plus additional High Level Terms or Preferred Term, if applicable
Anticholinergic events	Anticholinergic syndrome (narrow and broad search SMQ) Glaucoma (narrow search SMQ) Additional PTs: sinus tachycardia, supraventricular tachycardia, ventricular tachycardia, heart rate increased, palpitations, pupillary reflex impaired, pupils unequal, visual disturbance, constipation, gastrointestinal obstruction, ileus paralytic, urinary tract infection, cystitis, urinary incontinence, incontinence, dysuria, urge incontinence, urine flow decreased, bladder irritation, oropharyngeal pain, dysphonia, laryngitis, pharyngitis, and throat irritation
Pneumonia	All PTs that contain the term pneumonia

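### TEAE, on-treatment SAE and AESI summaries carry no exposure-adjusted rate, so if retention differs between arms the percentages would differ even with equal true risk

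*SAP*

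**What the plan says.** In SAP Section 4.2.5.3 the TEAE tables are patient-based: "The number and percentage of patients reporting any TEAE will be summarized", by SOC, HLT and PT, then by severity and by relationship. For the high-level categories, which include serious TEAEs, event totals are added: "Summaries on event counts will also be presented by categories above". These totals have no person-time denominator either.

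For the two AESI groups (anticholinergic events and pneumonia) the section says only: "The summaries on the following AESI will be produced by SOC and PT". No statistic is named, so the rule in Section 4.1 governs: "Categorical data will be summarized in terms of the number of patients providing data at the relevant time point (n), frequency counts and percentages".

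Section 3.5.2 closes the counting window: "An AE that occurs more than 15 days after the date of the last dose of double-blind IP will not be counted as a TEAE". The SAE subsection of 4.2.5.3 uses the same 15-day limit to separate on-treatment from off-treatment SAEs.

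The same subsection does use person-time for adjudicated cardiovascular events: "Number, percentage, and incidence (per 1000 patient-years of exposure to IP) of patients with adjudicated MACE".

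Treatment lasts at most 36 months in an event-driven study (Section 1.2). The sample size assumes 40% treatment discontinuation at year 2 (Section 1.3.1). Section 4.2.1 plans Kaplan-Meier curves and a log-rank test of time to IP discontinuation, and Section 4.2.3.1 a separate exposure summary. Neither is linked to the adverse event tables.

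**The concern.** A patient who stops drug after two months has about two and a half months in which a TEAE can be counted; a patient who stays to month 36 has three years. A percentage gives both the same weight in the denominator. It compares arms fairly only if time on drug is distributed alike in both.

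Overall safety is a stated objective (Section 1.1), and the general tables and AESI summaries are where a reader would look for anticholinergic or pneumonia signals. With unequal retention, the longer-exposed arm shows a higher percentage at the same true rate, and a real excess in the shorter-exposed arm is diluted. The table of common TEAEs is also selected by a crude percentage in either arm. Since the SAP already uses patient-years for adjudicated cardiovascular events, the omission elsewhere is a gap in coverage.

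**Working it through.** **Inputs from the SAP.** Maximum treatment 36 months (Section 1.2). From Section 1.3.1: treatment discontinuation 40% at year 2 with exponential times, 4000 patients, 1.9 MACE per 100 patient-years, 122 on-study and 91 on-treatment events, 6,500 patient-years. TEAE window of last dose + 15 days (Section 3.5.2).

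**Assumptions not in the SAP.** The split of discontinuation between arms (only one pooled figure is given); a constant adverse event rate of 0.10 per year, the same in both arms and independent of discontinuation; a common cut-off T for all patients.

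**The plan's own figure.** 122 / 0.019 = 6,421 patient-years, about 1% below the stated 6,500.

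**Mean time on drug.** With d the discontinuation proportion at year 2, the hazard is h = −ln(1−d)/2 and the mean time on drug is (1−exp(−hT))/h. At d = 40%, h = 0.2554. Three readings of exposure follow:
- every patient can reach 36 months: T = 3, mean 2.10 years;
- 6,500 / 4,000 = 1.63 years, matched by T = 2.10;
- on-treatment events: 91 / 0.019 = 4,789 patient-years, / 4,000 = 1.20 years, matched by T = 1.43.

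**Crude percentage.** With event rate L, P = L/(L+h) × (1 − exp(−(L+h)T)).

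For 35% versus 45%, h = 0.2154 and 0.2989. At T = 3:
- 35%: 0.10/0.3154 × (1 − exp(−0.946)) = 0.3171 × 0.6118 = 19.4%
- 45%: 0.10/0.3989 × (1 − exp(−1.197)) = 0.2507 × 0.6978 = 17.5%

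| Mean time on drug at 40% | 35% arm | 45% arm | Crude ratio |
|---|---|---|---|
| 2.10 years | 19.4% | 17.5% | 1.11 |
| 1.63 years | 15.4% | 14.2% | 1.08 |
| 1.20 years | 11.5% | 10.9% | 1.06 |

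Adding the 15-day window changes little: at T = 3 the figures become 19.7% and 17.8%, ratio 1.11, and no ratio in the table falls by more than 0.003.

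**Other splits at 0.10 per year.** 40% versus 40% gives 1.00. 37.5% versus 42.5% gives 1.05, 1.04 and 1.03 for the three exposure readings. 30% versus 50% at T = 3 gives 1.23.

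**Masking.** At T = 3, raise the true rate in the 45% arm by 12%, to 0.112 per year: 0.112/0.4109 × (1 − exp(−1.233)) = 19.3%, against 19.4% in the 35% arm. The excess disappears from the percentages.

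**Against sampling error.** With 2,000 per arm, 19.7% versus 17.8% is a difference of 1.9 points with standard error √[(0.197×0.803 + 0.178×0.822)/2000] = 1.23 points, about 1.5 standard errors.

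**The case against.** The strongest reply is that nothing in the SAP says retention will differ. The log-rank test in Section 4.2.1 shows that it will be examined, not that a difference is expected. This stands. A reader might infer that the better-retained arm will look less safe; the documents support only the conditional statement.

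The tables are descriptive, with no planned adverse event test, and the Kaplan-Meier curves, exposure summary and listing of relative start days would let a reader see an imbalance. This is true, but none of it supplies an adjusted figure.

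The main safety questions are already handled with time to event: MACE, MACE or other serious cardiovascular events, and all-cause mortality all use Cox models. This also stands and limits the gap to general TEAEs, on-treatment SAEs and AESIs.

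A reader might extend the point to every table in Section 4.2.5.3. Two do not fit:
- "Number and percentage of patients with any SAEs by SOC, HLT, and PT" is not confined to the 15-day window. SAEs are collected through post-treatment follow-up (Section 1.2), so that percentage depends on study retention (20% discontinuation assumed at year 2), not the 40% used above.
- "Number and percentage of patients with AEs leading to premature discontinuation of the IP by SOC and PT" concerns events that themselves cause discontinuation. The assumption of an event rate independent of retention fails, so this table should not be cited as showing the bias.

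Finally, the ratio of 1.11 requires that every patient can reach 36 months. At the exposure implied by Section 1.3.1 it is about 1.06 to 1.08.

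**Conclusion.** The point holds in conditional form. TEAEs, on-treatment SAEs and AESIs are summarized without exposure adjustment, although being counted depends on time on drug and the same section uses patient-years for adjudicated cardiovascular events. For an assumed 35% versus 45% split and 0.10 events per year the crude ratio is about 1.06 to 1.11; with equal retention it is 1.00. The split, the event rate, the constant hazard and the common cut-off are assumptions. For AESIs, the percentage format is inferred from Section 4.1, and the 15-day window is assumed because the AESI text states neither.

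The distortion is modest, and for most single terms it would be smaller than sampling error. The documents do not support a claim that the trial's safety conclusions are biased: no primary or secondary conclusion and no power figure is affected. This is a cheap improvement, best fixed before unblinding, while relative retention by arm is still unknown.

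**What to change.** Keep the percentages and add an exposure-adjusted column:
- For TEAEs, on-treatment SAEs and AESIs, report patients with a first event per 100 patient-years at risk, with time at risk from first dose to first event or last dose + 15 days.
- For the two AESI groups, add a rate ratio or rate difference with 95% CI.
- For any SAE, which includes off-treatment events, use on-study time as the denominator.
- In the AESI subsection, state the statistic and confirm that the TEAE window applies.

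The dates needed are already used to derive exposure and TEAE status, so no new data are required. The cost is programming and longer tables, plus a rate that is easy to interpret only if the hazard is roughly constant; a footnote should say so.

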#### **Deaths, Serious Adverse Events, and Other Significant Adverse Events**

An SAE that occurs on or after the date of the first dose of double-blind IP and within 15 days of the date of the last dose of double-blind IP will be considered an on-treatment SAE/TEAE.

An SAE that occurs after 15 days of the date of the last dose of double-blind IP will be considered an off-treatment SAE.

The following summaries will be produced:

- Number and percentage of patients with any SAEs by SOC, HLT, and PT
- Number and percentage of patients with adverse events with outcome of death by SOC and PT
- Number and percentage of patients with off-treatment SAEs by SOC, HLT, and PT
- Number and percentage of patients with AEs leading to premature discontinuation of the IP by SOC and PT

In addition, separate listings will be provided for the following:

- Deaths
- SAEs
- Permanent discontinuations of study treatment due to AEs

Adjudicated MACEs and other serious CV events of interest will be summarized as follows:

- Number, percentage, and incidence (per 1000 patient-years of exposure to IP) of patients with adjudicated MACE by MACE category, adjudicated subcategory, and PT (on-study analysis and on-treatment analysis).
- Number, percentage, and incidence (per 1000 patient-years of exposure to IP) of patients with adjudicated cardiac disorders (i.e. cardiac arrhythmias SMQ and cardiac failure SMQ) and cerebrovascular disorders by specific SMQ category and PT (on-study analysis and on-treatment analysis).
- Number, percentage, and incidence (per 1000 patient-years of exposure to IP) of patients with adjudicated non-fatal other CV events by PT (on-study analysis).

Supportive listings to summaries described above will be provided.

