### 3.1.7 Derived variables

#### 3.1.7.1 Rate of event

The rate of event per patient per year during a given period (e.g., during the first year of treatment) is calculated as the sum of all available events in that period divided by the sum of all patients follow-up time in that period, i.e.,  $\frac{\sum_{i=1}^n e_i}{\sum_{i=1}^n t_i}$ , where  $e_i$  is the number of event in patient  $i$  and  $t_i$  is the follow-up time in patient  $i$ . The follow-up time in patient  $i$ ,  $t_i$ , is calculated as  $d_i/365.25$ , where  $d_i$  is the number of days patient  $i$  exposed, calculated as (*follow-up date – randomization date + 1*).

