The on-study analysis is defined as all events that occurred while the patient was in the study, irrespective of treatment exposure (i.e., this includes all events that occurred during which the patient was on treatment or off treatment). The on-treatment analysis is defined as only events that occurred while the patient has received at least one dose of study double-blind IP during the treatment period excluding off treatment period/post treatment follow-up (PTFU) period.

The status of patients off treatment during the study period is referred to as the PTFU period.

**Handling professional/duplicate patients.** Professional patients are individuals who, in violation of protocol entrance criteria and enter into the same study more than once and/or enter into more than one study at the same or in close succession.

Unless otherwise stated, the first incidence of patient entering trial is used in analysis and summary. All data is listed for transparency, with flags for duplicate patients to ensure clarity which records are in/out of the analysis.

For handling of AEs, if a patient is on same treatment throughout (across all incidences), include all data in the analysis. If patient is on different treatments (i.e., different randomised treatment received at the second incidence vs the first incidence), the first incidence of patient entering trial is used in analysis.

**Handling data from patients with missing investigator signatures.** These patients will be excluded from the FAS and would be included in screened and randomized patient population.

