### **4.2.3 Extent of Exposure and Treatment Compliance**

#### **4.2.3.1 Extent of Exposure**

Exposure to the double-blind IP will be summarized for treatment duration (in days), calculated as *date of the last dose of the double-blind IP taken - date of the first dose of the double-blind IP taken + 1* (Analysis Population: FAS).

Duration of exposure before and after implementing the CSP amendment 2 will also be summarized.

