### **Analyses for COPD Exacerbations**

The rate of COPD exacerbations per patient per year (any, and moderate or severe) and rate of hospitalizations due to COPD exacerbations per patient per year will be analyzed using a Negative Binomial regression model (or Poisson regression model taking overdispersion into account for analyses that Negative Binomial regression does not converge) similar to the primary analysis of the primary efficacy variable. The exposure time will be re-calculated based on the last data collection during the whole study period.

The number of patients with at least one COPD exacerbation (any, mild, moderate, severe, and moderate or severe) will be analyzed based on a logistic regression model with treatment group, baseline ICS use, baseline COPD severity, history of at least one exacerbation in the past year, and smoking status as factors. The estimated treatment effect (i.e., the odds ratio of aclidinium over placebo), corresponding 95% CI, and two-sided p-value for the odds ratio will be presented. The model is as follows:

*Response (Yes=1/No=0) = treatment group + baseline ICS use + baseline COPD severity + history of at least one exacerbation in the past year + smoking status*

Time (in days) to first COPD exacerbation (any, and moderate or severe), time (in days) to second COPD exacerbation (any, and moderate or severe), time (in days) to third COPD exacerbation (any, and moderate or severe), time (in days) to first hospitalization due to COPD exacerbation, and time (in days) to withdrawal of the double-blind IP due to COPD exacerbation will be analyzed by means of Kaplan-Meier estimators and Cox Proportional Hazards model. The estimates of the hazard ratio comparing aclidinium with placebo will be derived using the Cox proportional hazard model for the time in terms of the number of days served as a response variable and treatment group, baseline ICS use, baseline COPD severity, history of at least one exacerbation in the past year, and smoking status as factors. The hazard ratio (aclidinium over placebo), corresponding 95% CI, and two-sided p-value for the hazard ratio will be presented. The model is as follows:

*Survival time = treatment group + baseline ICS use + baseline COPD severity + history of at least one exacerbation in the past year + smoking status*

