#### Sensitivity analysis

To account for the relation of the occurrence of an event and treatment exposure, an on-treatment analysis will be conducted and this will include only events that occurred while the patient was exposed to study treatment, i.e., events that occurred after the patient's last

treatment dose will be censored. Two ascertainment windows, 0 and 15 days, will be evaluated in the on-treatment analyses. The on-treatment and on-treatment +15 days analyses will censor events that occur after and more than 15 days after, respectively, after the last treatment dose (see Section 9.7.6.1 of the CSP for consideration on totality of evidence from on-study and on-treatment analyses in evaluation of MACE).

To assess possible effects of informative censoring, sensitivity analysis (on-study analysis) will be done as follows: based on the missing follow-up time in drop-outs, i.e. the time from censoring to study closure, the expected number of events that might have been observed if the drop-outs had completed the study can be calculated using an event rate similar to that observed in the study. The test (aclidinium versus placebo) will be recalculated with these residual events allocated in different proportions to the treatment groups to assess the robustness of the results with regard to the censoring of drop-outs.

Sensitivity analysis of the primary composite endpoint will also include analysis with CV death replaced with all-cause mortality.

**Subgroup analysis.** To evaluate the consistency in the primary safety endpoint over selected baseline characteristics, subgroup analysis will be performed. The subgroup is described below:

- History of at least one exacerbation in the past year ( $0, \geq 1$ )

The subgroup analysis on time to first adjudicated MACE will be analyzed using the same method as the primary analysis on the primary safety endpoint using a 95% CI and without statistical testing for NI (NI margin will not be used).

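### On-study incidence of adjudicated MACE and CV events is divided by patient-years on IP, so events after stopping IP are counted without the time in which they arose and the descriptive rates are overstated

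*SAP*

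**What the plan says.** Section 4.2.5.3, under deaths, SAEs and other significant AEs, lists three summaries of adjudicated events. The first, shown beside counts and percentages, is described as "incidence (per 1000 patient-years of exposure to IP) of patients with adjudicated MACE by MACE category, adjudicated subcategory, and PT (on-study analysis"; the on-treatment analysis is named there too. The second has the same denominator and the same two analyses, for adjudicated cardiac and cerebrovascular disorders. The third, again per 1000 patient-years on IP, is the incidence "of patients with adjudicated non-fatal other CV events by PT (on-study analysis" only).

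Section 4.1 fixes the numerator: "The on-study analysis is defined as all events that occurred while the patient was in the study, irrespective of treatment exposure". Section 1.2 says that patients who stop IP early stay under follow-up, and that MACE and SAEs are collected for the rest of the study.

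Section 4.2.3.1 fixes exposure to IP: "date of the last dose of the double-blind IP taken - date of the first dose of the double-blind IP taken", plus one day. It contains no time after the last dose.

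For rates of events, section 3.1.7.1 uses a different clock, with days per patient equal to "follow-up date – randomization date + 1".

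**The concern.** In the on-study rows the numerator and denominator cover different periods. A patient who stops IP at month 6 and has an MI at month 20 adds one event but only six months of time. The months in which the patient was off IP, under observation and at risk do not appear.

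Three things follow.

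- The absolute on-study rates of MACE and of the other CV events are too high in both arms. They also do not share the time scale of the on-study Kaplan-Meier curves and Cox model.
- On-study and on-treatment rates placed side by side on one denominator cannot be compared. The on-study rate can never be the lower of the two, even if events are rarer off treatment.
- If the arms stop IP at different speeds, the crude ratio of the two on-study rates is biased. The arm with less IP time looks worse. Section 4.2.1 plans a log-rank test of exactly this difference in discontinuation.

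MACE is the primary safety outcome, and these tables are where a reader will look for its absolute rate by category and preferred term.

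**Working it through.** **Inputs (SAP 1.3.1 unless stated).** 4000 patients; 1.9 MACE per 100 patient-years; IP discontinuation 40% and study discontinuation 20% at year 2; exponential times; stop at 122 patients with MACE. Follow-up per patient is not given. I assume a common follow-up T, chosen so that 122 events are expected, and vary it. I also assume the same MACE hazard on and off IP.

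**The plan's own figures.** Events = 4(z_0.975 + z_power)² / (ln 1.8)² (Schoenfeld) gives 121.7, so 122, at 90% power, and 90.9, so 91, at 80%. Both match the SAP. Patient-years = 122 / 0.019 = 6,421, against a stated 6,500.

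**Hazards per year.**
- Study withdrawal: −ln(0.8)/2 = 0.1116
- IP discontinuation, 40% read as all-cause: −ln(0.6)/2 = 0.2554
- IP discontinuation, 40% read as additional to study withdrawal: 0.2554 + 0.1116 = 0.3670

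**Mean time per patient.** m(h, T) = (1 − exp(−hT)) / h.

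**Follow-up that yields 122 events.** Solve 4000 × 0.019 × m(0.1116 + 0.019, T) = 122. This gives T = 1.80 years.

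| At T = 1.80 y | Patient-years | 122 events per 1000 PY |
|---|---|---|
| On-study follow-up, 4000 × m(0.1116, T) | 6,528 | 18.7 |
| IP exposure, all-cause reading, 4000 × m(0.2554, T) | 5,776 | 21.1 |
| IP exposure, additional reading, 4000 × m(0.3670, T) | 5,272 | 23.1 |

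Overstatement: 6,528 / 5,776 = 1.130 (+13%); 6,528 / 5,272 = 1.238 (+24%).

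**Time cut at the first MACE.** On-study 6,421 PY and IP 5,685 PY give 19.0 and 21.5 per 1000, ratio 1.129. Expected on-treatment first events are 0.019 × 5,685 = 108, so about 14 of the 122 fall off treatment.

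**Other follow-up times, all-cause reading.** The ratio is m(0.1116, T) / m(0.2554, T):

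| T (years) | 1 | 1.5 | 2 | 2.5 | 3 |
|---|---|---|---|---|---|
| Overstatement | 7% | 11% | 14% | 18% | 22% |

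With uniform accrual over an assumed 1, 2 or 3 years, a 36-month cap and closure at 122 events, it is 13%, 14% or 16%.

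**Unequal discontinuation (illustration).** Assume 35% on aclidinium and 45% on placebo at year 2, equal study withdrawal and a true ratio of 1. The IP hazards are −ln(0.65)/2 = 0.2154 and −ln(0.55)/2 = 0.2989. The crude rate ratio is then m(0.2989, T) / m(0.2154, T):
- T = 1.80 y: 1.393 / 1.493 = 0.93
- T = 3 y: 1.981 / 2.210 = 0.90

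A treatment with no effect on MACE would appear to lower the rate by 7% to 10%.

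**The case against.** **Loose wording.** Section 3.1.7.1 itself calls follow-up days exposed days, so the tables might be meant to use follow-up. But section 4.2.5.3 names IP, and it uses one phrase for both the on-study and the on-treatment rows. The phrase cannot suit both.

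**Little depends on it.** This largely stands. Sections 4.2.5.1, 4.2.5.2 and 4.2.5.8 plan on-study Cox analyses with the right clock for composite MACE, its components, the wider CV endpoint and all-cause mortality. Counts and percentages stand beside the incidences. With equal discontinuation both arms inflate alike and the ratio is preserved.

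**The percentage is not the SAP's own.** This stands too. Equal follow-up and the all-cause reading of the 40% are my assumptions, so the size is a range. Against the first-event clock of the Cox model, with IP time left uncut at events, the gap is 21.1 against 19.0, or about 11%.

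**Two further readings that a reader might infer, and that do not hold.**
- That the on-treatment rows are also mismatched. Section 4.2.5.3 says an SAE "within 15 days of the date of the last dose of double-blind IP will be considered an on-treatment SAE/TEAE", and section 4.2.5.1 says "Two ascertainment windows, 0 and 15 days, will be evaluated in the on-treatment analyses". But these rows carry the term on-treatment analysis. Section 4.1 defines it without off-treatment time, section 3.1.2 censors it at IP discontinuation, and section 4.2.5.1 gives the 15-day variant a separate name. The on-treatment rows match IP exposure as written.
- That section 4.2.4.3 sets a precedent for on-study time with "The exposure time will be re-calculated based on the last data collection during the whole study period". That section opens with an on-treatment default, so the sentence is not clean evidence. Section 3.1.7.1 is the better reference.

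**Conclusion.** The mismatch is explicit in the text, and the on-study incidences in all three summaries will be too high if the SAP is followed. The direction is certain as soon as any patient is followed after stopping IP.

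The size is conditional. It is about 13% with the planning inputs, equal follow-up of 1.80 years and 40% as all-cause discontinuation, and about 7% to 22% for common follow-up of 1 to 3 years under the same reading. It is about 24% at 1.80 years if the 40% is additional to study withdrawal, which section 1.3.1 does not settle. All of these assume an equal MACE hazard on and off IP. The bias between arms depends on a difference in discontinuation, and the 0.93 and 0.90 above are illustrations only.

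Two stronger conclusions are not supported. The non-inferiority test against 1.8 and the 122-event target are untouched, because the Cox model uses on-study time with the censoring of section 3.1.2. And 122/91 = 1.34 is not the inflation: 91 is the event count for 80% power, not the number of on-treatment events expected beside 122 on-study events, which is about 108 at 1.80 years.

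This should be corrected, but it is a matter of descriptive safety tables.

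**What to change.** In all three summaries of section 4.2.5.3, give the on-study rows their own denominator: patient-years of on-study follow-up per arm, from randomization to the on-study censoring or last follow-up date (sections 3.1.2 and 3.1.7.1). If first-event rates are intended, cut follow-up at the first event and say that denominators then differ by row. Keep IP-exposure years for the on-treatment rows only.

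The cost is a few words in the SAP and one on-study follow-up total per arm, or one per row for first-event rates. No new data are needed, and no model or event target changes. In the 122-event scenario the reported on-study MACE rate becomes 18.7 instead of 21.1 per 1000 patient-years on total follow-up, or 19.0 instead of 21.5 with both denominators cut at the first MACE.
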